9.8.2 Biomarker Assessments in Tumor Samples

Biomarker analyses in tumor samples at baseline and during treatment with GEN3009 monotherapy or GEN3009 + GEN3013 combination therapy may help confirm the MoAs of GEN3009 or GEN3009 combined with GEN3013 and enable the identification of biomarkers predictive of response to GEN3009 or GEN3009 + GEN3013. Tumor biopsies will be evaluated for CD37, CD3, and CD20 expression (protein or ribonucleic acid [RNA]), as well as molecular profiling to identify potential mechanisms of tumor response and/or treatment-induced changes in the immune microenvironment. The DNA that encodes the BCR expressed specifically by the cancer cells will be identified in the tumor biopsy at baseline to allow MRD assessment as described in Section 9.2.2.3.

9.8.2.1 Protein Expression Analyses

CD37, CD59, CD20, CD3 (combination arm), and expression of other proteins related to lymphoma biology [REDACTED] or GEN3009's MoA [REDACTED]

█ may be evaluated in tumor biopsies by IHC/immunofluorescence on an automated staining platform. Tumor sections will be scored by a certified pathologist, and digital images will be made from stained tumor sections in order to be used for exploratory digital pathology analyses.

9.8.2.2 RNA Expression Analyses

RNA sequencing may be performed on tumor biopsies to determine CD37, CD3, and CD20 RNA expression levels, as well as to evaluate other potential genes associated with CD37 biology [REDACTED] CCI [REDACTED] with immune effector cell activation, or with lymphoma biology in general, such as gene signatures characteristic of lymphoma subtypes [REDACTED] CCI [REDACTED] for exploratory biomarker analyses.

9.8.2.3 DNA Analyses

Tumor biopsies may also be analyzed using NGS for analyses of DNA mutations, copy number variations, microsatellite instability, indels, and/or rearrangements or polymorphisms [REDACTED] CCI [REDACTED] in genes associated with CD37 expression or function, [REDACTED] CCI [REDACTED] proposed MoAs of GEN3009 and GEN3013, or lymphoma biology, [REDACTED] CCI [REDACTED].

9.8.3 Biomarker Assessments in Blood Samples

Biomarker assessments will also be performed using whole blood samples to investigate safety markers and potential pharmacodynamic markers and explore the relationship to efficacy, AEs and/or MoA of GEN3009.

9.8.3.1 Immunophenotyping Analyses

Absolute counts of immune cells such as B cells (both benign B cells as well as circulating malignant cells), NK cells, monocytes, and T cells will be measured in whole blood and/or peripheral blood mononuclear cells (PBMC) samples using flow cytometry to monitor changes in frequency and/or phenotype (activation status) of these cells during GEN3009 monotherapy treatment. CD37 expression (in relation to mCRP expression), as well as CD37 occupancy by GEN3009, may be monitored to enable correlation analysis of target expression or GEN3009 binding with pharmacodynamic and efficacy assessments. The activation of immune effector cells (including NK cells, granulocytes and monocytes) may be monitored using activation markers such as CD69, CD25, or CD86, as well as markers related to effector function (such as CD16 or CD32 expression). For the GEN3009 + GEN3013 cohort additional immunophenotypes of circulating immune cells will be determined in fresh whole blood and/or PBMC samples using flow cytometry to monitor changes during GEN3009 + GEN3013 combination treatment. The T-cell activation and exhaustion phenotype will be evaluated using flow cytometry and markers such as CD69, CD25, and PD-1 in order to evaluate the association of such markers with drug target engagement, treatment efficacy and/or safety of GEN3009 + GEN3013. Additional immunophenotypes of circulating immune cells (eg, the levels of regulatory T cells which can suppress T-cell function) may be determined in fresh whole blood using flow cytometry to evaluate association of such markers with T-cell activation/exhaustion phenotype, patient response, and GEN3013's MoA.

9.8.3.2 Cytokine and Endothelial Activation Marker Analyses

As GEN3009 may activate immune effector cells or induce cytokine production resulting from lysis of immune cells and T-cell activation following initial GEN3013 administrations may lead to cytokine release causing CRS, cytokine levels will be monitored closely. The levels of cytokines, **CCI**

██████████ will be measured in plasma or serum samples. Additional cytokines and soluble markers of endothelial activation **CCI** █████ may also be determined to evaluate the association of such markers with treatment-emergent AEs and outcome to GEN3009 or GEN3009 + GEN3013.

9.8.3.3 Complement Analyses

As complement-mediated cytotoxicity is an anticipated key MoA of GEN3009, activation of the complement pathway will be assessed as a pharmacodynamics marker potentially predictive of clinical responses. Complement pathway activity will be monitored by CH50 measurements in serum, while individual complement pathway components such as C2 may be monitored in plasma for depletion following complement activation.

9.8.3.4 Cell-free DNA/RNA and Tumor-derived DNA (ctDNA) Analyses

Circulating cell-free DNA and/or RNA, including circulating tumor-derived DNA (ctDNA) and/or exosomal RNA (exoRNA), may be measured, and analyses such as RNA expression levels, DNA mutations, copy number variations, microsatellite instability, indels, and/or rearrangements in genes may be performed to evaluate the association of such biomarkers with the MoA of GEN3009, MoA of GEN3013, subject response, or lymphoma disease biology.

A saliva sample may also be evaluated to confirm the tumor specificity of any genomic alterations that are identified. Where required by local law, a separate consent will be used for DNA/RNA research.

If DNA/RNA research evaluations are performed, the results will be reported in a separate report.

10 SAFETY MONITORING AND ADVERSE EVENT REPORTING

10.1 Adverse Event Definitions

10.1.1 Definition of Adverse Events

An AE is any untoward medical occurrence in a clinical trial subject, temporally associated with the use of a medicinal product, whether or not considered related to the medicinal product. An AE can therefore be any unfavorable and unintended sign (including an abnormal laboratory finding), symptom, or disease (new or exacerbated) temporally associated with the use of a medicinal product.

AEs (including laboratory abnormalities that constitute AEs) should be described using a diagnosis whenever possible, rather than individual underlying signs and symptoms. When a clear diagnosis cannot be identified, each sign or symptom should be reported as a separate AE.

10.1.2 Definition of Serious Adverse Events

An SAE is defined as an AE that meets 1 of the following criteria:

- Is fatal or life-threatening¹
- Results in persistent or significant disability/incapacity
- Constitutes a congenital anomaly/birth defect
- Is medically significant, ie, defined as an event that jeopardizes the subject or may require medical or surgical intervention to prevent 1 of the outcomes listed above. Medical and scientific judgment must be exercised in deciding whether an AE is “medically significant”
- Requires inpatient hospitalization or prolongation of existing hospitalization² (Planned hospitalization for observation following GEN3009 and/or GEN3013 (GEN3009 + GEN3013 cohort 4 only) administration during Cycle 1 should not be reported as an SAE).

¹The term “life-threatening” in the definition of “serious” refers to an event in which the subject was at risk of death at the time of the event; it does not refer to an event which hypothetically might have caused death if it were more severe.

²Hospitalizations for the following reasons should not be reported as SAEs:

- Routine treatment or monitoring of the underlying disease, not associated with any deterioration in the condition
- Solely due to progression of the underlying cancer
- Elective or pre-planned treatment for a pre-existing condition that is unrelated to the underlying disease and has not worsened since signing the informed consent
- Social reasons and respite care in the absence of any deterioration in the subject’s general condition
- Treatment on an emergency outpatient basis that does not result in hospital admission and involves an event not fulfilling any of the definitions of an SAE given above is not an SAE.

10.1.3 Definition of Adverse Events of Special Interest

AESIs are defined as events (serious or non-serious) which are of scientific and medical concern specific to the sponsor’s product or program, for which ongoing monitoring and rapid

communication by the investigator to the sponsor may be appropriate. Such events may require further investigation in order to characterize and understand them.

AESIs are defined on the basis of an ongoing review of the safety data. AESIs are discussed further in Section [10.3](#) and in the IB.

10.1.4 Definition of Infusion-Related Reactions

IRRs are defined as any AEs occurring during infusion or where the onset of the event occurs within 24 hours after the ended infusion. For IRRs, the causality of the event should be judged as “related” by the investigator.

Investigators should consider the clinical picture and isolated events, such as “fatigue,” occurring within 24 hours after the end of infusion, and assess whether they do or do not constitute an IRR.

10.2 Adverse Event Reporting

All AEs, whether serious or nonserious (see definition in section [10.1.2](#)), will be documented from the first dose of GEN3009 and/or GEN3013 (GEN3009 + GEN3013 cohort only) until 30 days after the last GEN3009 and 60 days after the last dose of GEN3013, subject withdrew consent, subject started new anti-cancer treatment, or the subject died, whichever comes first. Refer to the electronic case report form (eCRF) completion guidelines for additional information on reporting and stepwise guidance.

Medical conditions (signs, symptoms, and diagnoses) that occur after the ICF is signed and prior to the first GEN3009 and/or GEN3013 dose should only be reported as AEs if they were assessed by the investigator to be caused by a protocol-mandated procedure (ie, tumor biopsy and/or CT scan), including washout or discontinuation of prior medications.

The investigator will use the CTCAE Version 5.0 ([NCI, 2017](#)) to describe the intensity of AEs, except for TLS (refer to [Appendix 4](#)), CRS (refer to [Appendix 13](#)) and ICANS (refer to [Appendix 14](#)). Changes in intensity of an ongoing AE should be assessed at each visit or more frequent if deemed necessary and must be reported.

SAEs still ongoing after the safety follow-up visit(s) should be followed on a regular basis according to the investigator’s clinical judgment until the event has been resolved or until the investigator assesses it as chronic and all queries have been resolved. Only SAEs judged by the investigator as related to GEN3009 (all cohorts) and/or GEN3013 (the combination cohort only) should be reported after the safety follow-up visit.

The investigator must assess whether or not the event is related to the trial drug. The relationship is to be judged using the following terms:

- Related
- Not related

If the relationship changes over time, the last judgment by the investigator should be reported. Relatedness has to be assessed and reported from the first time the event is being reported.

A suspected adverse reaction is one in which there is a reasonable possibility that the trial drug caused the AE; this means there is evidence to suggest a causal relationship between the trial drug and the AE (ie, considered related).

Note:

- Final assessment of AEs must be performed by a medically qualified person, ie, a medical doctor.
- All AEs that occur during the AE reporting period must be reported in a timely manner in the eCRF, whether or not the event is treatment-related.
- All AEs must be assessed at each visit (or more frequently, if necessary).

10.2.1 Pre-existing Condition

In this trial, a pre-existing condition (ie, a disorder that was present before the AE reporting period has started and noted on the medical history form) is not to be reported as an AE. If, however, a pre-existing condition worsens during the treatment period, the event must be reported as an AE in a timely manner in the eCRF.

10.2.2 Diagnosis

The diagnosis/cause of an AE should be recorded rather than the symptoms of the AE. If no diagnosis is available each sign and symptom should be recorded as individual AEs.

10.2.3 Disease Progression or Death

Progression of malignancy, if only documented by use of an appropriate method (as per CT/PET or MRI criteria), with no clinical symptoms, should not be reported as an AE or SAE. However, all hospitalizations and deaths caused by clinical manifestations of disease progression should be reported as SAEs.

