3 OBJECTIVES AND ENDPOINTS

Objectives and related endpoints are described for the Dose Escalation in [Table 17](#) and for the Expansion in [Table 18](#), [Table 19](#), and [Table 20](#).

Table 17 Objectives and Endpoints for Dose Escalation (GEN3009 for R/R B-cell NHL Including CLL/SLL)

OBJECTIVES	ENDPOINTS
Primary	

• Determine the MTD with and/or determine the RP2D of GEN3009• Evaluate safety and tolerability of GEN3009	
• Rate of DLTs• Frequency and severity of adverse events (AEs)/AESIs/SAEs• Changes in laboratory parameters• Changes in vital signs• Frequency of dose interruptions, dose delays, and dose intensity
Secondary	

• Establish PK profile of GEN3009• Evaluate immunogenicity of GEN3009• Evaluate preliminary anti-tumor efficacy of GEN3009• Evaluate preliminary clinical efficacy of GEN3009	
• PK parameters: clearance, volume of distribution and area under the curve (AUC) at different time points ($AUC_{7\text{days}}$, AUC_{last} and AUC_{inf}), maximum concentration (C_{max}), time to C_{max} (T_{max}), predose trough concentrations (C_{trough}), and half-life ($T_{1/2}$)• Incidence of neutralizing anti-GEN3009 antibodies (ie, ADAs)• ORR• CR rate• DoR• TTR• PFS• OS
Exploratory	

• Assess potential biomarkers predictive of clinical response to GEN3009 and evaluate potential surrogacy with PFS and OS• Assess pharmacodynamic markers related to MoA of GEN3009	
• CD37 expression• Minimal residual disease (MRD) status• Pharmacodynamic markers in blood samples (leukocyte subset frequencies and phenotype, target antigen expression, complement regulatory protein expression, plasma complement levels and activation [CH50], and cytokine levels)

Table 18 Objectives and Endpoints for Expansion (GEN3009 for R/R, DLBCL, FL, and CLL Cohorts)

OBJECTIVES	ENDPOINTS
Primary	
• Evaluate (preliminary) anti-tumor efficacy of GEN3009	• ORR
Secondary	
• Establish PK profile of GEN3009	• PK parameters: CL, AUC _{7days} , AUC _{last} , C _{max} , T _{max} , C _{trough} and T _{1/2}
• Evaluate safety and tolerability of GEN3009	• Frequency and severity of AEs/AESIs/SAEs • Changes in laboratory parameters • Changes in vital signs • Frequency of dose interruptions, dose delays, and dose intensity
• Evaluate clinical efficacy of GEN3009	• CR rate • DoR • TTR • PFS • OS

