9.2.3.2 Progressive Disease

Imaging findings suggestive of progressive disease (PD) despite evidence of clinical benefit have been described with immunomodulatory agents, eg, tumor flare or pseudo-progression ([Cheson et al., 2016](#)). Currently, the potential for similar effect of GEN3009 is unknown, but should be taken into consideration when evaluating imaging during the trial. Accordingly, an increase in the size of previously involved lymph nodes, especially at the beginning of GEN3009 treatment, may represent pseudo-progression and may not be designated as PD, unless there is continued increase in size on subsequent imaging studies or confirmed with biopsies. Hence, in order to avoid premature termination, subjects can remain on the GCT3009-01 trial at investigator and subject discretion until the response or lack thereof is confirmed on subsequent imaging.

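### Protocol Sections 10.1.2 and 10.2.3 give opposite SAE instructions for a hospital admission caused only by symptomatic disease progression

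*Protocol*

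**What the plan says.** Protocol Section 10.1.2 makes an AE serious if, among other criteria, it "Requires inpatient hospitalization or prolongation of existing hospitalization". Footnote 2 then lists kinds of hospitalization that are not to be reported as SAEs. Two entries matter here: "Routine treatment or monitoring of the underlying disease, not associated with any deterioration in the condition" and, separately, "Solely due to progression of the underlying cancer".

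Protocol Section 10.2.3 deals with progression directly. Progression shown only by imaging, "with no clinical symptoms, should not be reported as an AE or SAE". For everything beyond that it says "all hospitalizations and deaths caused by clinical manifestations of disease progression should be reported as SAEs".

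Neither section cites the other or says which prevails. The SAP tabulates serious and non-serious TEAEs separately (Section 11.1) and lists hospitalizations by subject (Section 11.9), but has no rule for progression-related admissions. It is also written to protocol version 4.0 and does not cover the combination cohort.

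The endpoint concerned is in Protocol Section 3. For Dose Escalation (Table 17) it is a primary endpoint: "Frequency and severity of adverse events (AEs)/AESIs/SAEs". For the combination safety run-in (Table 19) it is again primary: "Frequency and severity of AEs/AESIs/SAEs". The same endpoint is secondary in the monotherapy and combination Expansion cohorts (Tables 18 and 20).

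**The concern.** Take a subject admitted for pain, obstruction or general decline from growing lymphoma, where no other cause and no other seriousness criterion applies. Footnote 2 tells the site not to report an SAE. Section 10.2.3 tells the site to report one.

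The situation is foreseeable. Subjects have relapsed or refractory disease after at least two prior lines. AE collection continues for 30 days after the last GEN3009 dose and 60 days after the last GEN3013 dose unless new anti-cancer treatment, withdrawal of consent or death ends it sooner (Section 10.2). Admissions around the time of progression can therefore fall inside the window.

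Two things depend on the answer. The first is the count of subjects with an SAE, with a matching change in the non-serious tables. The second is whether the event reaches the sponsor within 24 hours (Sections 10.4.1 and 10.4.5). If sites follow different sections, part of any difference in SAE rate between cohorts or dose levels reflects reporting practice.

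**Working it through.** The plan states no figure to reproduce. The check is a comparison of the two rules, followed by simple division to show scale.

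**Step 1: apply both rules to each kind of event.**

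| Event | 10.1.2 with footnote 2 | 10.2.3 | Conflict? |
|---|---|---|---|
| Imaging-only progression, no symptoms | Not an SAE | Not an AE or SAE | No |
| Death from progression | SAE (fatal) | SAE | No |
| Symptomatic progression, admitted, also meets another criterion such as life-threatening | SAE on that criterion | SAE | No |
| Symptomatic progression, admitted, hospitalization the only criterion | Not an SAE | SAE | **Yes** |

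Only the last row is in dispute.

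**Step 2: look for a reconciling rule.** There is none in either section or in the SAP. Protocol Sections 10.2 and 10.4.1 refer to eCRF completion guidelines, which are not among the documents, so whether they settle the matter cannot be checked. Even if they do, the protocol text remains contradictory.

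**Step 3: trace what uses the serious label.**
- Affected: the SAE and non-serious AE tabulations (Protocol Section 11.4.1.1.1; SAP Section 11.1), 24-hour reporting, and follow-up beyond the safety visit, which Section 10.6 requires for every ongoing SAE.
- Not affected: DLTs, which Sections 7.2 and 7.3 define by grade, type and duration, and the 33% stopping criteria in Section 4.4.3, which concern IRRs, neutropenia, CRS and ICANS.

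**Step 4: scale per subject.** Inputs are the Expansion cohort size of 20 and the run-in size of 6 to 12 (Protocol Section 4.1). If one subject's only serious event is a disputed admission, SAE incidence changes by 1/N:
- N = 20: 1/20 = 5.0 percentage points
- N = 12: 1/12 = 8.3 percentage points
- N = 6: 1/6 = 16.7 percentage points

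The total effect is this step times the number of such subjects. The documents do not give that number, so no total is computed.

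**The case against.** The best defence is that the two sections can be read together. Section 10.2.3 concerns clinical manifestations of progression, not progression as such. Footnote 2 could then cover only admissions where progression itself is the sole reason, for instance a re-biopsy after symptom-free progression on imaging. The routine-care entry would not cover these, since it is confined to care without deterioration, so the progression entry would keep some content of its own.

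That reading is possible and would make a sensible rule, but it is not written down. Nothing in the footnote limits the entry to symptom-free cases, and a site applying its plain words would leave out a symptomatic admission. The entry would also do little work on that reading: an SAE must first be an AE, and Section 10.2.3 already says symptom-free progression is neither.

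The defence is right that the consequences are bounded. Footnote 2 removes only SAE status. Symptomatic events are still recorded as AEs whether or not related, so the committees can see them. No hypothesis test depends on the count (Section 11.4.2).

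Four stronger readings are tempting, and the documents do not support them.

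- *Progression deaths give the size.* The protocol's background on GCT3013-01 escalation (Section 2.1.4.2) reports 11 deaths from progression and 1 in its context, or 12/68 = 17.6% of subjects. Deaths are SAEs under both sections, so this does not measure the disputed category. Nothing in the documents supports any other assumed percentage of subjects with progression-only admissions.
- *A drug-induced tumor flare would be lost.* Section 9.2.3.2 says of pseudo-progression "Currently, the potential for similar effect of GEN3009 is unknown, but should be taken into consideration when evaluating imaging during the trial", but that concerns reading scans. Section 7.5.5 treats flare as a separately graded reaction and does not say that it mimics progression. A recognized flare is not solely due to progression. A loss would need an event misread, never reassessed, and serious only through hospitalization.
- *Dose decisions are compromised.* Step 3 of the working shows that the DLT rules and named stopping criteria do not use seriousness.
- *Comparison with GCT3013-01 SAE rates is invalidated.* No such comparison is planned, and that trial's SAE convention is not given.

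**Conclusion.** The contradiction is real and needs correcting. It is confined to symptomatic progression admissions whose only seriousness criterion is hospitalization. Within that category, two mandatory instructions disagree on a component of a primary endpoint in Dose Escalation and the safety run-in, and on expedited reporting in a first-in-human trial.

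The per-subject shifts in the working assume that the subject has no other SAE. They illustrate how sensitive small cohorts are and do not forecast the effect. This is an inconsistency in reporting wording, and it does not undermine the escalation design or the stopping rules.

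**What to change.** Reconcile the two passages into one rule for all sites. Either delete the progression entry from footnote 2 of Section 10.1.2, or limit it explicitly to admissions with no clinical manifestations of progression. Under either option Section 10.2.3 governs, and symptom-free progression on imaging stays unreported as now. This direction is preferable because a reported SAE can be set aside in analysis, whereas one that was never reported cannot be reliably recovered. Bring the eCRF completion guidelines into line.

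Optionally, add an eCRF flag for SAEs due to progression and present the SAE table with and without flagged events.

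The cost is one protocol edit and, if the option is taken, one eCRF field and one repeated table. The downside is a few more SAE forms and a slightly higher headline SAE rate.
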